6.24.2. Subjects with Elevations in Liver Transaminases or Bilirubin at Baseline

Drug-induced liver injury monitoring in subjects with elevations in liver transaminases or bilirubin at baseline should be performed throughout the study according to the procedures summarized below.

• If subjects with abnormal baseline liver indices develop elevations of ALT >3 × baseline or 300 U/L (whichever occurs first) during the study, repeat testing should be performed within 2 - 5 days.

- If there are persistent elevations (ALT >3 × baseline, or 300 U/L) upon repeat testing, then close observation (testing and physical examination 2 to 3 times per week) should be implemented and discontinuation of study drug should be considered.
- Discontinue the study drug if any of the following occur:
 - \circ ALT increases to >5 × baseline measurements or 400 U/L (whichever occurs first).
 - ALT increase $>3 \times$ baseline measurements or 300 U/L (whichever occurs first) AND the increase is accompanied by a concomitant increase in TBL to $> 2 \times$ ULN.
 - ALT increase >3 × baseline measurements or 300 U/L (whichever occurs first) with the appearance of fatigue, nausea, vomiting, right upper quadrant pain or tenderness, fever, rash, and/or eosinophilia (> 5%)

For any subjects who present with a constellation of syndromes indicative of liver disease as per the Investigator's overall assessment (i.e., fatigue, nausea, vomiting, right upper quadrant pain or tenderness, fever, rash, and/or eosinophilia [> 5%]), perform liver function tests to determine if liver disease is worsening.

Re-initiation of study drug may be considered after consultation with the Medical Monitor.

6.24.3. Close Observation for Suspected Drug-Induced Liver Injury

For all subjects, close observation for suspected drug-induced liver injury includes the following within 72 hours of suspected drug-induced liver injury:

- Repeating liver enzyme (ALT, AST, and alkaline phosphatase) and serum bilirubin tests 2 or 3 times weekly.
- The frequency of repeat testing can decrease to once a week or less if abnormalities stabilize or the study drug has been discontinued and the subject is asymptomatic.
- Obtaining a more detailed history of symptoms and prior or concurrent diseases.
- Obtaining a history of concomitant drug use (including nonprescription medications and herbal and dietary supplement preparations), alcohol use, recreational drug use, and special diets.
- Ruling out acute viral hepatitis types A, B, C, D, and E; autoimmune or alcoholic hepatitis; hypoxic/ischemic hepatopathy; and biliary tract disease.
- Obtaining a history of exposure to environmental chemical agents.
- Obtaining additional tests to evaluate liver function, as appropriate (e.g., INR, direct bilirubin).
- Considering gastroenterology or hepatology consultations.
- If biochemistries stabilize and the subject is asymptomatic, monitor liver biochemistries once a week until they return to baseline.
- Subjects who live far from study sites can be evaluated locally for history, physical exam, and laboratories, provided results can be communicated promptly to the site investigator.
6.25. Removal of Subjects from the Study

The Investigator may withdraw a subject from the study for any of the following reasons:

- Withdrawal of consent
- Non-compliance as determined by the Investigator
- At the discretion of the Investigator and/or study Medical Monitor and/or the DMC if it is in the best interest of the subject
- Lost to follow-up

At any time, the Investigator can remove a subject from the study drug and/or the study if deemed necessary for subject safety. The Sponsor also reserves the right to terminate the study at any time. All data normally collected at completion of the study must be collected at the time of the subject's early termination or termination of the study.

The Investigator will discuss with the subject or legally acceptable representative(s) the most appropriate way to withdraw to ensure the subject's health. Should a subject (or a legally acceptable representative) request or decide to withdraw consent, all efforts will be made to complete and report the observations as thoroughly as possible up to the date of withdrawal.

7. PLANNED STATISTICAL METHODS

7.1. Endpoints

7.1.1. Efficacy Endpoints

7.1.1.1. Primary Endpoint

The primary endpoint (Main Study Only) is the absolute change from baseline in hepatic fat fraction measured by MRI-PDFF at Week 12

7.1.1.2. Secondary Efficacy Endpoints

Main Study: The secondary endpoints are:

- Absolute change from baseline in hepatic fat fraction measured by MRI-PDFF at Week 22 24
- Percent change from baseline in hepatic fat fraction measured by MRI-PDFF at Weeks 12 and 22 24
- Responder: subjects who achieved a clinically meaningful relative reduction of at least 30% in liver fat content as measured by MRI-PDFF at Week 12
- Responder based on NAFLD Activity Score (NAS) system: subjects who had a decrease of ≥ 2 points in NAS with at least a 1-point reduction in either lobular inflammation or hepatocellular ballooning and with no concurrent worsening of fibrosis stage
- Change from baseline in ALT at Weeks 12, 16 and 20

Cohort C: The secondary endpoints are:

- Change from baseline in liver stiffness as evaluated by FibroScan® at Week 16
- Changes from baseline in non-invasive biomarkers including Pro-C3 at Weeks 12, 16 and 20, and liver fibrosis by ELF[™] Test score at Weeks 6 and 16

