3. INVESTIGATIONAL PLAN

3.1. Overall Study Design and Plan

This is a Phase 2a, randomized, double-blind, placebo-controlled study evaluating the safety and efficacy of EFX in subjects with NASH.

Main Study: Subjects meeting the study's entry criteria will be randomly assigned in a 1:1:1:1 ratio into 4 treatment groups as shown in Figure 2 below:

Figure 2.Study Schema – Main Study

Randomization will be stratified by baseline hepatic fat fraction (< 15% vs \geq 15%) and F1 fibrosis score. Study drug will be administered subcutaneously once weekly (QW) for a total of 16 weeks. After 16 weeks of treatment, a safety follow-up visit will occur at Week 20. Subjects with \geq 30% relative fat reduction on MRI-PDFF at week 12 will be required to return between weeks 22 - 24 for a repeat liver biopsy and MRI-PDFF.

Cohort C: Subjects meeting the study's entry criteria will be randomly assigned in a 1:2 ratio into 2 treatment groups as shown in Figure 3 below:

Figure 3. Study Schema – Cohort C

Following 16 weeks of treatment, subjects will be given the option to collect an end of treatment biopsy.

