7.4. Data Handling Conventions

Missing data can have an impact on the interpretation of the trial data. In general, values for missing data will not be imputed.

Where appropriate, safety data for subjects that did not complete the study will be included in summary statistics. For example, if a subject received study drug, the subject will be included in a summary of AEs according to the treatment received; otherwise, if the subject is not dosed then they will be excluded from the summary. If safety laboratory results for a subject

are missing for any reason at a time point, the subject will be excluded from the calculation of summary statistics for that time point. If the subject is missing a pre-dose value, then the subject will be excluded from the calculation of summary statistics for the pre-dose value and the change from pre-dose values.

Values for missing safety laboratory data will not be imputed; however, a missing baseline result will be replaced with a screening result, if available. If no pre-treatment laboratory value is available, the baseline value will be assumed to be normal (i.e., no grade [Grade 0]) for the summary of graded laboratory abnormalities.

Values for missing vital signs data will not be imputed; however, a missing baseline result will be replaced with a screening result, if available.

Further details of data handling conventions and transformation will be provided in the SAP.

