7.6.2. Secondary Efficacy Analysis

Main Study:

Akero Therapeutics, Inc.

For the continuous secondary efficacy variables related to hepatic fat fraction, like percent change from baseline in fat fraction measured by MRI-PDFF at week 12, the same ANCOVA model used for primary efficacy variable will be used. For the other continuous secondary efficacy variables, the ANCOVA model with treatment group, baseline hepatic fat fraction (< 15% vs \geq 15%), and F1 fibrosis score as factors will be used. Normality will be tested for the model residuals. For certain efficacy variables, logarithmic transformation may be performed prior to fitting the ANCOVA model.

For the responder(s) based on MRI-PDFF, logistic regression will be used for the analyses. The analyses will include the treatment group and F1 fibrosis score as factors and baseline hepatic fat fraction measured by MRI-PDFF as a covariate. The missing value will be imputed as a non-responder.

For the responder(s) based on the NAS system, Fisher's exact test will be used for the analyses. Odds ratios, 95% confidence intervals and p-values will be provided. The missing value will be imputed as a non-responder.

Cohort C:

Summary statistics (number of subjects, mean, standard deviation, median, minimum, and maximum) at all visits and change from baseline will be provided. The efficacy variables will be analyzed with an ANCOVA model with treatment group as a factor and baseline value as a covariate. The effect of Type 2 diabetes status will be explored. Normality will be tested for the model residuals.

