- a All visits after Baseline (Day 1) can be performed within the following window: ± 3 days for weekly visits 1 20. Other windows are indicated below.
- b Complete PE including assessment at Screening, Baseline and Weeks 12 and 16, symptom driven at weeks 1, 4, 8, 20, or ET. CP Score assessments should be completed as part of the physical exam at Baseline, Week 12, Week 16, ET and Week 20.
- c Vitals to include systolic and diastolic BP, pulse, respiration rate, and oral temperature (at Screening and Baseline only) will be collected at each visit.
- d Triplicate BP/HR at Baseline and at 48 96 hours post-dose on Weeks 4 and 8 to correspond to C_{max}. BP/HR to be measured in same arm with at least two minutes rest between measurements.
- e Liver biopsy obtained within 180 days of randomization to confirm eligibility.
- f MRI-PDFF and ELFTM will be performed during screening, at Weeks 6 and 12 ± 5 days. Corrected T1 will be collected, where available.
- g If the Baseline questionnaires are missed at Day 1, questionnaires should not be collected at the remaining timepoints. The following questionnaires will be administered: HRQoL include: SF-36, CLDQ-NAFLD, WPAI. It is recommended that the questionnaires be completed prior to any study procedures being performed and prior to the subject seeing a health care provider.
- h AE reporting during screening is limited to SAEs and AEs related to study procedures.
- i Refer to Table 3. At visits where CTX-1 or lipids are collected, the samples to be collected in the morning following an overnight fast of at least 8 hours.

- j PK sampling will be obtained pre-dose at all timepoints listed and at 48-96 hours post-dose on weeks 4 and 8 to correspond to C_{max}.
- k Samples will be obtained for detection of ADA against EFX and if required a neutralizing ADA assay will be run on the same sample.
- 1 Pre-baseline labs should be collected 4 weeks post-Screening.
- m Saliva cortisol testing will be obtained pre-dose at all timepoints listed and at 48 96 hours post-dose on Weeks 4 and 8 to correspond to C_{max}.
- n For female subjects of childbearing potential only. Serum pregnancy test at screening and urine pregnancy test at other time points.
- o Subjects with \geq 30% relative fat reduction on MRI-PDFF at Week 12 will be required to return at Week 22 24 for a repeat liver biopsy and MRI-PDFF. The biopsy and MRI-PDFF should be collected within 5 working days of one another. The window for this visit is - 6 weeks.

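### As written, the Week 22-24 MRI-PDFF comparison with placebo uses only Week 12 responders, so it does not estimate the randomised effect, and the direction of its bias is unknown

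*Protocol*

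**What the plan says.** Protocol section 7.1.1.2 names two Main Study secondary endpoints at the late visit: "Absolute change from baseline in hepatic fat fraction measured by MRI-PDFF at Week 22 24" and "Percent change from baseline in hepatic fat fraction measured by MRI-PDFF at Weeks 12 and 22 24".

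The scan is not taken in everyone. Section 3.1 says that subjects with at least a "30% relative fat reduction on MRI-PDFF at week 12 will be required to return between weeks 22 - 24", and footnote o of Appendix A repeats that this group "will be required to return at Week 22 24 for a repeat liver biopsy and MRI-PDFF". The synopsis gives the same rule. No section schedules a Week 22-24 MRI-PDFF for anyone else. Footnote o adds: "The window for this visit is - 6 weeks".

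For analysis, section 7.6.2 states: "For the continuous secondary efficacy variables related to hepatic fat fraction" (percent change at Week 12 is its example), "the same ANCOVA model used for primary efficacy variable will be used". It makes no exception for Week 22-24. Section 7.6.1 says that this model estimates each active dose against placebo.

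On missing data, section 7.4 says: "In general, values for missing data will not be imputed". Multiple imputation is specified in 7.6.1 for the primary variable only. Corrected T1 at Week 22-24 (section 7.1.1.3) has the same timing, and section 7.6.3 gives it the same analysis as the secondary variables.

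The SAP supplied covers Cohort C. Its introduction says that a separate SAP exists for the Main Study.

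**The concern.** Followed literally, the protocol compares EFX and placebo at Week 22-24 in subsets chosen after randomisation, and chosen on an earlier value of the outcome being compared. The arms were randomised; the responders within them were not. To cross the 30% line, a placebo subject needs a fall well beyond the average for that arm, while an EFX subject can cross it with an average fall. The two subsets therefore differ in how extreme their Week 12 values are. Adjusting for baseline fat does not remove this, because selection acts on the change after baseline.

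The estimate would look like the Week 12 analysis (same model, same contrast) but would answer a different and poorly defined question. A reader could take it as evidence that the benefit had persisted, faded or reversed.

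**Working it through.** **Inputs from the documents.** SD of change 5.2, difference 5 points, 20 per arm (section 7.10). Placebo change -1.3 in the cited pegylated FGF21 trial (section 1.5). Entry requires at least 10% liver fat (section 4.2).

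**Assumptions, not in the documents.** Baseline fat normal with mean 19 and SD 6, truncated at 10%. The cited trial's absolute and relative changes imply baselines of 6.8/0.38 = 17.9, 5.2/0.26 = 20.0 and 1.3/0.06 = 21.7. The correlation between Week 12 and Week 22-24 changes is ρ_P on placebo and ρ_E on EFX. The share of effect retained at Week 22-24 is varied.

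**Reproducing the plan's figure.** The noncentrality is 5 / (5.2 × √(2/20)) = 3.04. A one-sided 5% t-test on 38 df has power 0.910, which matches the stated 91%. The SD and effect are therefore used as the protocol uses them.

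**Who qualifies.** At baseline 19 the threshold is a change of -0.30 × 19 = -5.7.
- Placebo: k = (-5.7 + 1.3)/5.2 = -0.846, so Φ(k) = 0.199, about 4 of 20.
- EFX (mean -6.3): k = (-5.7 + 6.3)/5.2 = 0.115, so Φ(k) = 0.546, about 11 of 20.

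Over the baseline distribution, simulation gives 20% and 53%. About 21% of simulated trials have two or fewer placebo responders.

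**Expected responder-only difference.** With λ = φ(k)/Φ(k), λ_P = 0.2789/0.1987 = 1.403 and λ_E = 0.3963/0.5459 = 0.726. Then

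estimate = true difference + 5.2 × (ρ_P λ_P − ρ_E λ_E).

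With equal ρ the shift is 5.2 × 0.677 × ρ = 3.52ρ: +1.76, +2.47 and +3.17 for ρ = 0.5, 0.7 and 0.9. Simulation with 400,000 subjects per arm, fitting treatment and baseline fat in responders only, agrees:

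| True Week 22-24 difference | ρ = 0.5 | ρ = 0.7 | ρ = 0.9 |
|---|---|---|---|
| about -5 (all retained) | -3.3 to -3.1 | -2.6 to -2.5 | -1.9 to -1.7 |
| -2.5 (half retained) | -0.8 | -0.1 | +0.7 |
| 0 (none retained) | +1.7 | +2.4 | +3.1 |

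The ranges in the first row reflect whether the simulated fall is capped at the subject's baseline fat. In single trials of 20 per arm with the effect fully retained, one-sided 5% power is about 90% if everyone is scanned and 17% to 26% in responders only.

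**Unequal correlations.** With ρ_P = 0.3 and ρ_E = 0.9 the shift is 5.2 × (0.3 × 1.403 − 0.9 × 0.726) = 5.2 × (0.421 − 0.653) = -1.21, so a true -5 becomes about -6.2. With 0.3 and 0.7 it becomes about -5.4. With 0.4 and 0.8 it stays near -5.0.

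**Change from Week 12 in responders.** If nothing truly changes after Week 12, the expected apparent change is 5.2 × λ × (1 − ρ). At ρ = 0.5 that is 5.2 × 0.726 × 0.5 = +1.9 on EFX and 5.2 × 1.403 × 0.5 = +3.6 on placebo. Simulation for ρ = 0.5, 0.7 and 0.9 gives +1.9, +1.1 and +0.4 on EFX and +3.5, +2.1 and +0.7 on placebo. This rebound is pure regression to the mean.

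**The case against.** The strongest answer is that the governing document is not in view. The protocol leaves detailed methods and data handling to the SAP, and the Main Study SAP may define a population and method for Week 22-24. Section 7.6.2 does not itself say that the model is fitted in responders only; that follows from the scan schedule plus the no-imputation rule. LS means and p-values are spelled out in 7.6.1 for the primary variable only. This limits the point to the protocol text, which still needs an exception.

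Second, a reader might infer that the bias must run against EFX, that a maintained benefit would look about halved, or that a vanished one would show EFX as worse. Those results hold under equal correlations. If placebo responses persist less well than EFX responses, the bias can disappear or favour EFX. The documents give no correlations, so no direction is supported.

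Third, a reader might infer that the trial cannot address Week 22-24 at all. That is too strong. Whether a scan is taken depends on an observed Week 12 value, apart from dropout. Regressing Week 22-24 on baseline and Week 12 within arm, then predicting for everyone, recovers -5.0 and 0.0 in the same simulation model. It does so by extrapolating across the 30% cut, from about four placebo subjects. The same holds if 7.6.2 is read as carrying over the primary imputation. The protocol specifies no such analysis for this endpoint.

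Finally, the stakes are modest: section 7.10 calls the study exploratory, the objectives in 2.2 name only Week 12 for MRI-PDFF, and the fixed testing sequence is described only for the primary variable.

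**Conclusion.** The point stands on the protocol text. Sections 7.1.1.2, 7.6.2 and 7.4 and the scan rule together produce a dose-versus-placebo comparison in subjects selected on Week 12 fat, and that is not the randomised treatment effect. The distortion can be as large as the effect of interest: up to about 3 points toward or past zero under equal correlations of 0.5 to 0.9, and about 1 point in favour of EFX at 0.3 and 0.9. Its sign and size in this trial are unknown.

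The figures rest on the protocol's SD, effect and cited placebo change, and on assumed baseline fat, correlations and retention. The simulations treat one dose against placebo, omit the F1 factor and cover absolute change only; percent change and cT1 were not simulated. The Week 12 analyses are unaffected.

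**What to change.** In 7.1.1.2 and 7.6.2, exempt the Week 22-24 absolute and percent MRI-PDFF changes from the ANCOVA comparison with placebo. Do the same for Week 22-24 cT1 in 7.1.1.3 and 7.6.3.

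Report these measures descriptively by arm in Week 12 responders: value and change from baseline, with n and the actual time since last dose, and no between-arm estimate or p-value. Time since dose matters because Appendix A shows no dose at Week 16. Nominal Weeks 22-24 therefore fall 7 to 9 weeks after a Week 15 dose, but the window of minus 6 weeks could bring the scan to Weeks 16-18.

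State that the subjects were selected on Week 12 MRI-PDFF, so any change from Week 12 includes regression to the mean and must not be presented as durability. Keep Week 12 as the only randomised MRI-PDFF comparison, in line with 2.2. Check that the Main Study SAP says the same.

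The cost is wording, with no extra scans, and the loss of a between-arm p-value at Week 22-24.

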7.1.1.3. Exploratory Efficacy Endpoints

The exploratory endpoints are:

- Change from baseline in markers of liver injury and function including AST, ALP, GGT, bilirubin, INR, albumin, MELD score, and CP score at Weeks 12, 16 and 20
- Change from baseline in body weight and waist-to-hip ratio at Weeks 12, 16 and 20
- MRI-PDFF based quantitation of hepatic fat (Main Study only)

- Changes from baseline in non-invasive biomarkers including Pro-C3 at Weeks 12, 16 and 20, and liver fibrosis by ELF[™] Test score at Weeks 6 and 12 (Main Study Only)
- Change from baseline in bone mineral density of the lumbar spine, femoral neck, and total hip as measured by DXA at Week 16
- The proportion of subjects at Week 22 24 (Main Study) and Week 16 (Cohort C) whose fibrosis regresses by ≥ 1-stage according to the NASH CRN classification
- The proportion of subjects at Week 22 24 (Main Study) and Week 16 (Cohort C) who had no worsening in NAS with improvement in fibrosis stage
- The proportion of subjects at Week 22 24 (Main Study) and Week 16 (Cohort C) who had 2 points improvement in NAS with no worsening in fibrosis stage
- The proportion of subjects at Week 22 24 (Main Study) and Week 16 (Cohort C) who had ≥ 1point improvement in NAS, fibrosis, steatosis lobular inflammation or hepatocellular ballooning
- Changes from baseline in HRQoL (SF-36, CLDQ-NAFLD, WPAI) at Weeks 12 and 16
- Change from baseline in lipoprotein profile and markers of lipid metabolism, insulin sensitivity and glycemic control at Weeks 12, 16 and 20
- Change from baseline in body fat distribution as measured by DXA total body composition at Week 16
- Changes from baseline in corrected T1 (cT1), an MRI-based metric of fibro-inflammation at Weeks 12 and 22 24 (Main Study only)
- Plasma concentrations of EFX
- The incidence of the decompensated liver disease events including ascites, hepatic encephalopathy (HE), or variceal bleeding (Cohort C Only)

7.1.2. Safety Endpoints

The safety endpoint is safety and tolerability of EFX in subjects with NASH.

Safety analyses include: summaries of extent of exposure, AEs, laboratory evaluations, ECG, and vital sign assessments, body weight, anti-drug antibody (ADA) and neutralizing antibody (NAB) assessments, and concomitant medication usage.

7.2. Analysis Conventions

All individual subject data will be listed as measured. All statistical summaries and analyses will be performed using Statistical Analysis System (SAS[®]) software (SAS Institute, Cary, North Carolina, USA).

7.3. Analysis Sets

7.3.1. Efficacy

The primary analysis set for efficacy analyses will be the Full Analysis Set (FAS) which includes all subjects who were randomized into the study.

Subjects who receive a dose of study drug other than that to which they were randomized for the entire duration of treatment will be analyzed according to treatment group to which they were randomized.

7.3.2. Safety

The primary analysis set for safety analyses will be the Safety Set which includes all subjects who received at least one dose of study drug. Subjects who received a dose of study drug other than that to which they were randomized for the entire duration of treatment will be analyzed according to the dose of study drug received.

All data collected during treatment plus 30 days after last dose of study drug will be included in the safety summaries.

